4.4.2 Blood sampling

Sterile, disposable tubes with a stopper will be used for the collection of blood samples for complete blood count. A 30-mL sample of venous blood should be drawn before the beginning of the infusion (time point 0, pre-dose).

Once the infusion begins, venous blood collection will continue at the following time points:

- 1 h, 3 h, 5 h, 5.5 h, 6 h, 7 h, 8 h, 10 h, 12 h from the beginning of the infusion for the pharmacokinetic study.

- Day 35 from the beginning of infusion for immunogenicity study.
- 1 h, 3 h, 5 h, 5.5 h, 6 h, 7 h, 8 h, 10 h, 12 h from the beginning of the infusion for the enzymatic activity study

Once the infusion finishes (visit II), volunteers will be observed until 20:00 p.m, the same day. Then, they will be discharged to return to their homes.

For immunogenicity sample collection: At visit II, racks with 2 2-mL polypropylene tubes with stoppers will be prepared to separate serum from each volunteer in two samples (sample and counter sample) from each collection time point for anti-agalsidase beta antibody measurement, immunogenicity measurement.

After collecting the blood sample, tubes will be allowed to reach room temperature for 30 minutes to separate the clot and serum. Then they will be centrifuged at 2000g for 15 minutes to separate the serum.

To receive the serum, polypropylene tubes will be used. Each serum sample will be separated into 2 aliquots (sample and counter sample) to measure immunogenicity.

For pharmacokinetic sample collection: At visit II, racks with 10 2-mL polypropylene tubes with stoppers (heparinized tubes) will be prepared for each volunteer for the separation of plasma into two samples (sample and counter sample) applicable to each collection timepoint for the quantification of agalsidase beta, pharmacokinetics measurement. After collecting the blood sample, tubes will be kept cold and then centrifuged at 4 °C at 8000 rpm for 10 min for plasma separation.

Sample quantification will be carried out in an independent laboratory. The mass of agalsidase present in each sample will be quantified.

For sample collection for enzyme activity: At visit II, the same tubes used for PK measurement will be used for each volunteer. An aliquot of the plasma separated at each time point will be used for measuring enzyme activity.

After collecting the blood sample, tubes will be kept cold and then centrifuged at 4 °C at 8000 rpm for 10 min to separate the plasma.

Biological activity will be measured by the fluorimetry method in plasma samples, obtained in heparin tubes.

To receive the serum, polypropylene tubes will be used. Each serum sample will be separated into 2 aliquots (sample and counter sample) for agalsidase beta, enzyme activity or immunogenicity measurements. Tubes will be labeled with the study code, volunteer number and collection time points.

The complete process from the blood sample collection to obtaining the 2 (two) aliquots of serum will take 60 minutes. Tubes will be frozen at -20 °C at the Site's laboratory and will be taken after each hospitalization by Biosidus for their storage until measurements are made.

Criteria for rejecting a sample: pronounced hemolysis, accidental thawing.

All tubes for blood collections, and polypropylene tubes for serum collection will be labeled with a self-adhesive label where the study code, volunteer number and collection timepoint will be indicated.

Storage of Plasma and Serum Samples

Serum or plasma obtained at each time point will be placed in duplicate in polypropylene tubes properly labeled and stored at -20 °C in a secured freezer with temperature control, at the Site laboratory, with restricted access to the staff until its transfer to Biosidus.

4.4.3 Analytical Method

Samples

All serum or plasma samples will be stored in duplicate at -20°C. Before the assay, the samples should be allowed to reach room temperature (15 °C - 28 °C) and mixed by gentle stirring. Aliquots from the samples will be made to prevent freezing - repeated thawing. The duplicate shall be kept at -20 °C.

Quantification Method

Pharmacokinetic Quantification:

Samples will be shipped at -20°C to Shin Nippon Biomedical Laboratories (SNBL), Ltd.

The agalsidase content will be quantified by the electrochemiluminescence method. The SNBL laboratory will validate the quantification method before the study is initiated.

Enzyme Activity Quantification

For the measurement of the biological enzyme activity in the plasma samples, the fluorimetric method of hydrolysis of the synthetic substrate 4-MU-Gal will be used.

Immunogenicity Measurement

Serum samples will be incubated with 1 ng beta agalsidase for 15 minutes at room temperature. Then, the sample enzymatic activity will be measured using the 4-MU-Gal substrate.

The inhibition percentage of the samples will be determined by comparing the activity value of 1 ng agalsidase beta with the treated samples. Those samples with percentage inhibition > 50% will be designated as positive.

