SPONSOR	Biosidus S.A. [name] [contact] [contact]
PRINCIPAL INVESTIGATOR	[name] [name] [contact]
CO – INVESTIGATOR	[name]
REGULATORY HEAD	[name]
SITE	Sanatorio Nuestra Señora del Pilar [name]
LABORATORIES	
 • Enzyme Activity Assessment: Biosidus Development Department - [name], Argentina - [contact] - [contact] • Immunogenicity Assessment: Biosidus Development Department - [name], Argentina - [contact] - [contact] • Pharmacokinetic Assessment: Shin Nippon Biomedical Laboratories, Ltd., [name], [contact]; [contact]
PRIMARY OBJECTIVE	Compare the pharmacokinetic behavior of Biosidus Agalsidase beta and Fabrazyme® (Genzyme) after administration by intravenous infusion of 1 mg/kg over a period of 5 hours of one of the following formulations: - Fabrazyme®, by Sanofi Genzyme (Reference Formulation, "R") - Agalsidase beta, biosimilar developed by Biosidus SA (Test Formulation, "T")

SECONDARY OBJECTIVE	Evaluation of enzyme activity, product safety, incidence of adverse events and tolerance. Evaluation of antibody occurrence.
STUDY DESIGN	Open, randomized, parallel-arms, balanced, single-dose, and sequential
DISCONTINUATION SCHEDULE	The sponsor and investigators may independently discontinue the study at any time at the sole possibility or occurrence of a serious adverse event or situation that could affect the volunteer's health.
NUMBER OF VOLUNTEERS	A total of 20 (twenty) male volunteers will initially be included. As it is a sequential design, if the statistical analysis on the first 20 volunteers does not demonstrate bioequivalence, an additional number of healthy volunteers to be determined will be included to verify the similarity criterion with adequate power.

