1.1.3 Pharmacokinetics

Following intravenous administration of agalsidase beta to adults dosed at 0.3 mg, 1 mg, and 3 mg/kg of body weight, AUC values increased more than dose-proportionally due to decreased clearance, which indicated saturated clearance. The elimination half-life was not dose-dependent and ranged from 45 to 100 minutes.

Following intravenous administration of agalsidase beta to adults with an infusion time of approximately 300 minutes and dosed at 1 mg/kg/body weight, every two weeks, mean plasma C_{max} ranged from 2,000 to 3,500 ng/mL, while that the $AUC_{0-\infty}$ ranged from 370 to 780 mcg.min/mL. The mean volume of distribution at steady state ranged from 8.3-40.8 L, plasma clearance from 119-345 mL/min. and the mean elimination half-life from 80 to 120 minutes.

Beta agalsidase is a protein and is predicted to be metabolically degraded by peptic hydrolysis. Therefore, hepatic impairment is not expected to impact on the pharmacokinetics of agalsidase beta in a clinically significant manner. Renal clearance of agalsidase beta is considered a secondary clearance pathway.

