1.1.6 Warnings

Immunogenicity:

As agalsidase beta (recombinant human α -galactosidase A or r-haGAL) is a recombinant protein, development of IgG antibodies is expected to occur in patients with little or no residual enzyme activity. In studies that resulted in the approval of the reference medicine, most patients developed IgG antibodies to r-haGAL, mainly within 3 months of the first drug infusion. Over time, most seropositive patients in clinical trials showed a decreasing trend in titers (based on a \geq 4-fold reduction in titers from peak measurement to the last measurement) (40% patients) or they showed tolerance (no detectable antibody was confirmed by 2 consecutive radioimmune precipitation assays (RIPA)) (14% patients) or showed a plateau (35% patients). Healthy volunteers participating in this study, whose enzyme activity is normal, are expected to have little or no antibody response to agalsidase beta administration.

Infusion-Related Reactions:

Patients with antibodies to recombinant agalsidase beta (recombinant human α -galactosidase A or r-haGAL) are more likely to experience infusion-related reactions (IRRs) defined as any related adverse effect occurring on the day of the infusion. These patients should be treated with caution when re-administering agalsidase beta. Antibody status in patients with Fabry disease and on treatment should be monitored regularly.

Hypersensitivity

Allergic hypersensitivity reactions may occur, as with any other protein medication for intravenous administration.

If serious allergic or anaphylactic reactions occur, agalsidase beta administration should be discontinued immediately and appropriate treatment should be initiated. Current standards for emergency medical treatment of this situation will be followed.

Patients with Advanced Kidney Disease

The renal effect of agalsidase beta treatment may be limited in patients with advanced kidney disease.

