At each time point, 30 mL of blood will be drawn, which will be placed in adequate tubes to obtain serum or plasma, as appropriate (for example, up to 500 mL of blood is drawn from a volunteer blood donor at a time and without consequences for him/her).

Samples to be obtained from each volunteer will be drawn from the contralateral arm to which the infusion of the experimental drug is being made.

After verifying its correct operation, the pre-dose sample (hour 0) will be drawn. Next, the intravenous administration of the corresponding infusion will begin according to the order of randomization.

Sampling times during Visit II will be the following:

1. For pharmacokinetic analysis: predose (0 hour), 1 h, 3 h, 5 h, 5,5 h, 6 h, 7 h, 8 h, 10 h, 12 h from the beginning of infusion.
2. For enzyme activity analysis: predose (0 hour), 1 h, 3 h, 5 h, 5,5 h, 6 h, 7 h, 8 h, 10 h, 12 h from the beginning of infusion.
3. For immunogenicity analysis: predose (0 h), 12 h and day 35.

On the study day, volunteers will be allowed to drink fluids freely.

Alcoholic drinks or xanthines will not be allowed (since 48 hours before the test).

No medication (neither allopathic nor homeopathic) will be allowed during the two weeks prior to the study.

Snacks during Visit II:

During hospitalization, volunteers may consume only standardized food, provided by the clinic. No other type of food will be allowed other than that which complies with the guidelines that are developed below:

Meal	Time Schedule	Menu
Lunch	4 hrs after the beginning of the infusion (approximately between 12 and 12:30 p.m.)	A piece of chicken (breast or leg and thigh), with no skin A portion of white rice 500 mL of mineral water 1 sachet of salt 1 small package of crackers 1 apple.
Afternoon snack	8 hrs after the beginning of infusion (approx. 4:00 p.m.)	1 cup of coffee or tea (decaffeinated with 100 mL of whole milk), 2 butter croissants each with 2 cooked ham slices and 2 cheese slices.
Dinner	12 hrs after the beginning of the infusion (approx. 8:00 p.m.)	A piece of chicken (breast or leg and thigh), with no skin A portion of white rice 500 mL of mineral water 1 sachet of salt 1 small package of crackers 1 apple.

VISIT III, IV, V y VI (phone contact):

The principal investigator or the delegated medical staff will contact the volunteer by telephone after visit II to ask about tolerance to medication and the occurrence of adverse events on days 3, 7, 14 and 21 after visit II respectively.

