8 IMMUNOGENICITY ANALYSIS

The incidence of anti-agalsidase beta antibodies will be determined both at the start of treatment, at the end of visit II and 31 days after the end of the infusion, for both treatment groups.

Serum samples will be incubated with 1 ng agalsidase beta for 15 minutes at room temperature. Then, the enzyme activity for the samples will be determined using the 4-MU-Gal substrate.

The inhibition percentage of the samples will be determined by comparing the activity value of 1 ng agalsidase beta with the treated samples. Those samples with percentage inhibition > 50% will be reported as positive.

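### The antibody rule states no correction for enzyme already in the serum, so it leans towards antibody-negative, potentially strongly at 12 h

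*Combined protocol and SAP*

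**What the plan says.** Section 4.4.3 (Immunogenicity Measurement) describes the assay in four steps.

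- Spike: "Serum samples will be incubated with 1 ng beta agalsidase for 15 minutes at room temperature".
- Readout: enzyme activity on the 4-MU-Gal substrate.
- Comparison: "The inhibition percentage of the samples will be determined by comparing the activity value of 1 ng agalsidase beta with the treated samples".
- Call: "Those samples with percentage inhibition > 50% will be designated as positive".

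Section 8 repeats the rule and ends: "Those samples with percentage inhibition > 50% will be reported as positive". Neither section mentions a well of the same serum without spike, subtraction of pre-dose or native activity, removal of drug, a drug-tolerance limit, or the serum volume or dilution. No other antibody assay is described.

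Section 4.4.1 sets the sampling times: "For immunogenicity analysis: predose (0 h), 12 h and day 35". Section 8 places the last sample 31 days after the infusion instead. The difference does not affect this point, and that sample is called the end-of-study sample below.

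Two background statements bear on the assay. Section 1.1.3 gives pharmacokinetic figures for this dose and infusion length. Section 1.1.6 describes the subjects as "Healthy volunteers participating in this study, whose enzyme activity is normal".

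**The concern.** The readout is total enzyme activity. Enzyme that was in the serum before the spike adds signal, and the formula counts that signal as absence of inhibition. There are two sources: residual drug at 12 h, and the volunteers' own enzyme at every time point. Both push computed inhibition down, so the 50% cut-off is stricter in practice than it appears.

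Antibody induction is a secondary objective (section 2), and the Protocol Summary plans to compare it between formulations. The error favours finding no antibody. At 12 h it also varies with each volunteer's residual drug, so the antibody reading is mixed with the pharmacokinetics that the trial is comparing.

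**Working it through.** The documents state no residual level, drug tolerance or serum volume, so there is no plan figure to reproduce.

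**Inputs**

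- Spike 1 ng, positive above 50% inhibition: sections 4.4.3 and 8.
- Infusion "1 mg/kg over a period of 5 hours" (Protocol Summary, primary objective), so 12 h is 7 h, or 420 min, after it ends.
- Cmax 2,000–3,500 ng/mL, and "the mean elimination half-life from 80 to 120 minutes": section 1.1.3, for 1 mg/kg over about 300 min.
- A second half-life range of 45–100 min across 0.3, 1 and 3 mg/kg: section 1.1.3.
- Serum volume: not stated. Assumed 10, 50 and 100 µL, undiluted.
- Further assumptions: Cmax occurs at the end of infusion, decline is mono-exponential, and residual drug is as active per ng as the spike.

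**1. What the rule returns.** Let E be the ng of active enzyme already in the well and i the fraction of enzyme neutralised.

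- Measured activity = (E+1)(1−i), in ng-equivalents.
- Computed inhibition = 1 − (E+1)(1−i).
- With no antibody (i = 0) this is −E, which is below zero.
- A positive needs (E+1)(1−i) < 0.5, so i > 1 − 0.5/(E+1).
- At E = 0 the requirement is 50%, as intended. At E = 1 it is 75%.

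**2. Residual drug at 12 h** = Cmax × 2^(−420/half-life).

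- 80 min: 2,000 × 0.0263 = 53 ng/mL.
- 120 min: 3,500 × 0.0884 = 309 ng/mL.
- 45 min: 2,000 × 0.00155 = 3.1 ng/mL, and 3,500 × 0.00155 = 5.4 ng/mL.

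On the 80–120 min range, 2.6–8.8% of Cmax remains. As a cross-check, the section 1.1.3 clearance (119–345 mL/min), an assumed 60–80 kg man and the same half-lives give 15–198 ng/mL. For example, 60,000,000 ng / 300 min / 345 mL/min = 580 ng/mL, and 580 × 0.0263 = 15 ng/mL.

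**3. Neutralisation needed for a positive at 12 h**, from 1 − 0.5/(E+1):

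| Assumed serum | E at 45 min | Needed | E at 80–120 min | Needed |
|---|---|---|---|---|
| 10 µL | 0.03–0.05 ng | 52–53% | 0.5–3.1 ng | 67–88% |
| 50 µL | 0.16–0.27 ng | 57–61% | 2.6–15.5 ng | 86–97% |
| 100 µL | 0.31–0.54 ng | 62–68% | 5.3–30.9 ng | 92–98% |

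At 50 µL the whole range is about 57–97%.

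**4. If antibody neutralises only the spike** and residual enzyme stays active, the maximum computed inhibition is 1 − E. A positive is then impossible once E reaches 0.5 ng. That takes 500/309 = 1.6 µL to 500/52.6 = 9.5 µL of serum on the 80–120 min range, but 92–161 µL at 45 min.

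**5. Other time points.** Pre-dose serum contains no drug. By day 35, (35 × 1,440 − 300)/120, about 417 half-lives, have passed, so residual drug is nil. Native enzyme remains in both samples; the documents give no figure for it.

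**6. Effect of the fix.** Spiked minus unspiked activity = (E+1)(1−i) − E(1−i) = 1−i, so inhibition on the difference equals i for any E. With true i = 60% and E = 1 ng, the written rule gives 1 − 2 × 0.4 = 20% (negative) and the difference gives 60% (positive).

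**The case against.** The strongest reply is that section 4.4.3 is a method summary. It does not exclude a blank, and it does not say whether the 1 ng reference is read in buffer or in serum. The laboratory method may already correct for background. This is fair about what the laboratory may do. But sections 4.4.3 and 8 give a complete decision rule, and followed as written that rule does not apply a 50% neutralisation cut-off.

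A reader might go further and infer that the 12 h sample must be negative whatever the antibody status. The documents do not support that. Serum volume and dilution are unknown, a pre-dilution would shrink the effect, and the 45 min half-life leaves the requirement near 50% for small volumes. Antibody in sufficient excess to neutralise residual drug and spike together would still read positive.

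The timing objection also stands in part. The 12 h sample comes 7 h after the end of a first and only infusion. Section 1.1.6 says that patients mostly developed IgG within three months of the first infusion, and it expects little or no response in these volunteers. A negative is likely at 12 h under any rule. A reader might also infer that this negative will be presented as proof of no immunogenicity. The plan does not say so: section 8 only reports incidence, with no acceptance criterion. The primary pharmacokinetic conclusion is unaffected.

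**Conclusion.** The concern holds as a bias, not as a forced result. As written, the formula understates inhibition whenever enzyme is already in the serum, at all three sampling times.

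At 12 h the bias is potentially large. A positive needs about 57–97% neutralisation instead of 50%, given an assumed 50 µL of undiluted serum, mono-exponential decline from Cmax, and antibody acting equally on residual drug and spike. The upper part of that range rests on the half-life reported with this dose and infusion time; the lower part uses the 45 min figure. A 12 h negative is therefore uninformative, but the practical harm is limited because little antibody is expected so early.

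The pre-dose and end-of-study samples, which carry the information on induced antibody, are biased in the same direction by native enzyme only. The documents do not allow that amount to be estimated. The plan should be corrected because a secondary objective depends on this rule and the remedy is small.

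**What to change.** In sections 4.4.3 and 8:

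1. Run each serum with and without the 1 ng spike, and define inhibition as 1 − (spiked minus unspiked activity)/(activity of the 1 ng standard).
2. State the serum volume and dilution in the well.
3. Report the 12 h sample as not evaluable because of residual drug, unless drug tolerance to about 310 ng/mL is shown. Subtraction alone is not enough there: it cannot recover antibody already bound to drug, and it is imprecise when E far exceeds 1 ng. At E = 15.5 ng, an assumed 3% error in the spiked reading is 0.03 × 16.5 = 0.5 ng, half the spike.
4. Base antibody incidence on the end-of-study sample compared with the same volunteer's pre-dose sample.
5. Describe the endpoint as enzyme-neutralising antibodies, since the assay cannot detect antibodies that bind without inhibiting activity.

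The cost is 20 volunteers × 3 samples = 60 extra wells if read singly, plus three for each volunteer added under the sequential design, and the revised wording. No new visits or blood draws are needed.

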4.5 VOLUNTEER FOLLOW-UP

The study will be conducted under medical supervision and all the information will be transcribed to the Medical Record and the CRF.

During the hospitalization period, the volunteer will undergo a permanent clinical evaluation by the principal investigator and his group of collaborators.

Before each blood draw, blood pressure, heart rate and respiratory rate will be measured. In the pre-dose and final draw, hematocrit will also be recorded. These data together with the theoretical and real times of collection will be recorded in the Medical Record and will be transcribed to the Case Report Form (CRF).

During the study, signs and symptoms of intolerance to the medication must be observed, which will be documented in the Medical Record and the CRF.

4.7 SAMPLE IDENTIFICATION

Collection tubes:

Tubes must be identified with the study protocol code (RD-BIO-AGA-01/03/21) at the top, then the patient identification code (NNXXxxxxxx) must be placed, then two letters that will identify the type of quantification to be made on the sample (pharmacokinetics: PK, enzyme activity: AE or Immunogenicity: IM), then a two-digit number that corresponds to the sample number.

EXAMPLE:

RD-BIO-AGA-01/03/21

04PJ270560: PK 10

In this case, this sample applies to a pharmacokinetic quantification, to the tenth sample from volunteer number 04.

Aliquot tubes:

The aliquot number will be added to the above information (sample: A1 or counter sample: A2) with a digit followed by the letter A.

EXAMPLE:

RD-BIO-AGA-01/03/21

04PJ270560: PC 10 A1

In this case, this sample is to perform the pharmacokinetic quantification of Aliquot 1 of the tenth sample from volunteer number 04.

The types of sample obtained in this study are detailed below:

Table 1 PK Samples (PK)

Table 2 Samples for Enzymatic Activity (EA)

Table 3 Immunogenicity Samples (IM)

Timepoint Days)	(h or 0 h	12 h	Day 30
Sample	1	10	3
Aliquot 1	A1	A1	A1
Aliquot 2	A2	A2	A2

5 CRITERIA FOR SCREENING VOLUNTEERS

5.1 POPULATION

In order to be selected and included in the study, volunteers must meet all the screening and inclusion criteria and none of the exclusion criteria.

The number of subjects to be included in the study will be a total of 20 male volunteers. As a sequential study, additional volunteers may be included.

Those volunteers who meet all the inclusion criteria and none of the exclusion criteria will be incorporated into the study, after having explained the purpose of the clinical trial and having signed the informed consent for participation.

Presence of the following inclusion criteria and absence of exclusion criteria must be verified by the Principal Investigator in the medical record and in the applicable form in the CRF book of each subject.

